1.3.7 Criteria for discontinuation

Participants may withdraw at any time by refusing to participate in further assessments or by electing not to continue with pregnancy termination.

We expect loss to follow up for all primary and most secondary outcomes to be rare as most assessments are made on the date of study enrollment. We expect some loss to follow up for the POD1 assessment but will take the following steps to minimize this loss: testing of participant phone numbers at the time of enrollment, providing a reminder about the phone call prior to clinic discharge, agreeing in advance on a convenient time for the follow up phone call, providing participants with the study coordinators phone number, and provision of a gift card by mail after completion.

Patients who experience serious adverse events will be discontinued from the study and allocation may be revealed to ensure appropriate management of medical conditions. An adverse event (AE) is defined as any health-related reaction, effect, toxicity or abnormal laboratory result that a study participant experiences during the course of the study, irrespective of relationship to the study intervention. A serious adverse event (SAE) is defined as any experience that is fatal or life threatening, requires in-patient hospitalization or prolongation of an existing hospitalization, or results in a persistent or significant disability or incapacity.

A data safety monitoring board (DSMB) will be assembled. A DSMB meeting will be triggered by a case of respiratory compromise requiring sedation reversal (naloxone or flumazenil). This board will consist of clinicians and researchers knowledgeable in abortion care, moderate sedation, and gabapentin. The following individuals have agreed to serve on the DSMB:

- [name], Professor of Obstetrics and Gynecology, Division Director of Family Planning, University of California Davis

- [name], MPH, Senior Director of Medical Services, PPFA
- [name], PhD, Professor of Anesthesia/Dean, University of California San Francisco

If triggered to meet, they will review the cumulative data to date and provide advice regarding the safety of continuing, modifying, or discontinuing the study.

The study may be discontinued at any time by IRB or clinical management at either participating institution or the Office for Human Research Protection. One of the co-investigators (AB) will review all adverse events. If there is a suspicion for increased risk, study allocation may be revealed for a preliminary analysis and if related to the study intervention, the study could be prematurely ended.

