1.1.2 Objectives and hypotheses

Objective 1: To compare the effect of gabapentin 600 mg to placebo on intraoperative pain during D&E under moderate sedation.

We hypothesize that administration of gabapentin will lower reported pain during D&E compared to placebo.

Objective 2. To compare the effect of gabapentin 600 mg to placebo on the total dose of IV sedation (fentanyl and midazolam) during D&E.

We hypothesize that administration of gabapentin will reduce the total dose of IV sedation agents compared to placebo.

Objective 3. To compare the effect of gabapentin 600 mg to placebo on pre- and post-operative pain, anxiety, nausea, vomiting, and overall satisfaction with pain management.

We hypothesize that administration of gabapentin will result in lower pre- and post-operative pain, anxiety, nausea, and vomiting, and higher satisfaction with pain management compared to placebo.

Objective 4. To compare the adverse events and risks of gabapentin to placebo.

We hypothesize that pre-operative administration of gabapentin will not increase adverse events compared to placebo.

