1.3 Design and methodology

1.3.1 Research design and General Methodological Approach

We propose a randomized controlled double-blinded trial comparing oral gabapentin 600 mg to placebo among patients undergoing outpatient same-day dilation and evacuation under moderate sedation. We propose to give the study drug (gabapentin or placebo) shortly after the initiation of same-day cervical preparation and a minimum of one hour prior to D&E. The primary study outcome is maximum pain during D&E as recorded by 100-mm VAS (Table 1). Secondary outcomes include total doses of IV sedation, pain at three time points during D&E, perioperative pain, anxiety, nausea, vomiting, patient satisfaction with pain management, oxygen saturation during moderate sedation, and administration of sedation reversal agents. We will also contact patients by phone on post-operative day 1 (POD1) to assess for prolonged or delayed side effects, adverse events and overall satisfaction with pain control.

Study medications will be administered by study staff, Planned Parenthood of Metropolitan Washington DC (PPMW) staff, or MedStar Washington Hospital Center (MWHC) staff after initiation of cervical preparation. The MedStar Health Research Institute (MHRI) pharmacy will prepare identical capsules containing gabapentin 600 mg or methylcellulose placebo. The pharmacy will package the capsules in sequentially numbered opaque sealed envelopes according to a computer-generated 1:1 randomization scheme prepared by MHRI. Study staff involved in administering medications and assessing outcomes, clinical staff (health care associates, nurses, physicians), and participants will be blinded to randomization assignment. Randomization assignment will only be revealed at the time of data analysis or in the case of a serious adverse event. As there is no standard or optimal dose of pre-operative gabapentin, we have chosen to use a dose of 600 mg with the aim of maximizing pain relief while minimizing the sedative effect. This is the same dose currently being investigated during first-trimester abortion at Emory University.

Administration of analgesics, anesthetics, and anti-emetics will be standardized. Patients will generally receive the following oral pre-procedure regimen: naproxen 500 mg, ~~tramadol 50 mg,~~

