1.3.5 Admission procedure

After eligibility has been confirmed and informed consent has been obtained, participants will complete a questionnaire assessing demographic information and medical history (Appendix C). Relevant baseline characteristics including age, gravidity, parity, race, ethnicity, and weeks of gestation will be collected. We will also document pre-existing psychiatric disorders such as depression, anxiety, bipolar disorder and chronic pain syndromes.

She will then be assigned to the next sequentially numbered randomization packet. After initiation of cervical preparation, the participant will consume the study drug from the packet with water or clear juice. Time of administration will be recorded on the patient's chart and will occur at least one hour before the planned procedure. All medications given throughout the clinic experience will be recorded. Method(s) of cervical preparation will be recorded. Antibiotic, anti-emetic, and analgesic administration will be standardized but medications may be adjusted to the need of each woman to accommodate patient characteristics such as allergies and without regard to her enrollment in this study.

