1.3.6 Follow-up procedure

The pre-operative assessment will be completed by the study coordinator immediately prior to initiation of moderate sedation (Appendix D), which usually occurs in the procedure room. The intra-operative assessments will be administered by the study coordinator during the procedure at the specified time or point during the procedure (Appendix E). The times of all assessments will be noted. The time of speculum removal will be considered the time of procedure completion.

A same-day post-operative assessment will be completed by the participant 30 minutes (20-40 min range) after procedure completion in the recovery room (Appendix F). After completion of the post-operative assessment patients will receive a \$40 gift card and be reminded that they will receive a phone call the following day.

A phone call will be made to all participants on the day following their procedure to administer the POD1 assessment (Appendix G). The participant phone number will be tested at the time of enrollment and three attempts will be made to reach participants by phone on POD1. Participants will be provided with a phone number for the study coordinator should they have trouble receiving phone calls. Patients that complete the POD1 assessment will be mailed a \$10 gift card.

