1.3.10 Data analysis

Data analysis will be conducted using Stata. The baseline characteristics of the populations will be described. Intention-to-treat analysis will be performed. Primary continuous outcome (pain score on 100-mm point VAS) for the two treatment groups will be compared using T-tests, and if appropriate, by non-parametric analysis. Secondary outcomes will be compared using Chi-square and T-tests, as applicable. Baseline characteristics will be evaluated for potential interaction or confounding with primary and secondary outcomes. If we observe 5 serious adverse events (SAE) requiring sedation reversal agents before enrolling 50 participants, we will ask the statisticians to unblind allocation and

perform an interval analysis to assess for a relationship between study arm and risk of SAE. Once 50 participants are enrolled, we will ask the same analysis after 6 events occur. These numbers of events are based on the concept that if all of the events are in one treatment arm we would find a statistically significant difference in SAE risk between the arms. For reference, sedation reversal is used in less than 1% of D&Es at both sites. Participants may request that their data not be used for analysis if a request is received prior to analysis as mentioned in the consent form. MedStar Health Research Institute (MHRI) statisticians will be consulted to assist with the analysis as needed.

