1.6 Main problems anticipated

The frequency of intraoperative pain assessments will require the study coordinator to remain in the room throughout the procedure and therefore we will limit recruitment to 4 patients per day per site to minimize disruptions to clinic flow. This will also reduce the chance of missing data from

perioperative assessments as a result of the coordinator's unavailability. We also anticipate some loss to follow up at the time of the POD1 assessment; this assessment is a secondary outcome and we are taking steps to minimize loss as described in section 1.3.6. Our final concern relates to the potential for over-sedation with the combination of gabapentin and opioids, which could impact both patient safety and clinic flow if discharge is delayed. Although dose-finding studies have not identified an ideal dose, we suspect that a one-time dose of 600 mg will improve pain control without significantly contributing to sedation. Sedation reversal agents are available at both sites. Adverse events, including respiratory depression, will be monitored, reviewed, and allocation revealed if necessary.

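### Section 1.3.7 takes women with a serious adverse event out of the study after a single dose already taken, which conflicts with the day-1 call to every participant and weakens the safety objective

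*Combined protocol and SAP*

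**What the plan says.** All references are to the combined protocol and SAP.

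- Section 1.3.7 (Criteria for discontinuation): "Patients who experience serious adverse events will be discontinued from the study and allocation may be revealed". The purpose given for revealing allocation is medical management. The section does not say which assessments continue after such an event.
- The same section, on voluntary withdrawal: "Participants may withdraw at any time by refusing to participate in further assessments". Its other route out is a decision not to go on with the termination.
- Section 1.6 describes the intervention as a single administration: "we suspect that a one-time dose of 600 mg will improve pain control". Section 1.3.5 says that the time of administration "will occur at least one hour before the planned procedure".
- Section 1.3.6: "A phone call will be made to all participants on the day following their procedure". No exception is made for a serious adverse event. Section 1.3.1 gives the purpose of the call: "to assess for prolonged or delayed side effects, adverse events and overall satisfaction with pain control".
- Section 1.1.2, Objective 4: "To compare the adverse events and risks of gabapentin to placebo".
- Section 1.3.10: "Intention-to-treat analysis will be performed". No method for missing scores is given.

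**The concern.** In a trial with repeated dosing, discontinuation after a serious adverse event can mean that the drug stops while follow-up goes on. Here the drug has already been taken, so the rule cannot reduce exposure. What remains to be discontinued is data collection.

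Read that way, a woman with an intra-operative event would lose her 30-minute assessment and her day-1 contact. If the event came before the 3-5 minute point after speculum removal, she would lose the primary maximum-pain score as well. The day-1 call is where prolonged or delayed effects are sought, and these are the women in whom such effects matter most for Objective 4.

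The loss is also not random. It is triggered by an outcome that Objective 4 compares between arms, and section 1.6 names over-sedation with gabapentin plus opioids as a concern. Loss that may depend on arm is the kind that an intention-to-treat label does not repair.

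**Working it through.** **1. Setting the sections side by side**

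| Question | Section | Answer |
|---|---|---|
| Is study drug left to stop? | 1.3.5, 1.6 | No: one dose, at least 1 hour before D&E |
| What happens after an SAE? | 1.3.7 | Discontinued from the study |
| Who gets the day-1 call? | 1.3.6 | All participants, no exception |
| What is the call for? | 1.3.1 | Delayed side effects, adverse events, satisfaction |
| How are data analysed? | 1.3.10 | Intention to treat, no missing-data method |

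For a woman with an SAE, sections 1.3.6 and 1.3.7 cannot both be followed on the natural reading.

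Who falls under the rule is also not fully clear. Section 1.3.7 defines an SAE as fatal, life-threatening, requiring or prolonging hospitalisation, or disabling. Section 1.3.10 applies the term to events needing a sedation reversal agent, which that definition does not name.

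**2. The plan's own sample size**

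Inputs from section 1.3.11: difference 13, SD 25, alpha 0.05 (taken as two-sided), power 80%.

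n per arm = 2 × (1.960 + 0.842)² × 25² / 13² = 58.05, rounded up to 59. This reproduces the stated 59 per arm and 118 in total. Enrolling 130 allows 130 − 118 = 12 losses (9.2%).

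**3. How many women**

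The documents give no SAE rate. The nearest figure is sedation reversal in under 1% of D&Es at both sites (section 1.3.10). Taking a range of rates p as an assumption, the expected number is 130p and the chance of at least one is 1 − (1 − p)^130:

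| Assumed p | Expected of 130 | P(at least one) |
|---|---|---|
| 0.5% | 0.65 | 48% |
| 1% | 1.3 | 73% |
| 2% | 2.6 | 93% |
| 5% | 6.5 | 99.9% |

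At 1%, the binomial chance of 2 or fewer in 130 is 86%, and the chance of 3 or more in a given arm of 65 is 2.8%. Rates of 2% and 5% lie above anything documented and stand in for a possible drug effect.

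**4. Effect on power**

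Power = Φ(13 / [25 × √(1/n₁ + 1/n₂)] − 1.960), with n₁ = 65 and all losses in the other arm:

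- none lost: 84.2%
- 1 lost: 84.0%
- 3 lost: 83.4%
- 6 lost: 82.4%
- 12 lost: 80.2%

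**5. Effect on the primary mean**

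If k of 65 women in one arm are lost, and their scores would have averaged d points away from the mean of those retained, the arm mean shifts by k × d / 65. Both k and d are assumptions:

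- k = 1, d = 25: 0.4 points
- k = 1, d = 50: 0.8 points
- k = 3, d = 25: 1.2 points
- k = 3, d = 50: 2.3 points, or 2.3/13 = 18% of the target difference

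The sign of d is not known. A heavily sedated woman might report little pain, and a woman with a complicated procedure might report a great deal.

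**The case against.** The strongest reply is that the sentence never says that assessments stop, that the call is cancelled or that data are dropped. The line on withdrawal says how a participant may leave; it does not define what discontinuation by the investigators involves. Section 1.3.6, with its call to everyone, could equally show that contact continues. This stands in part: the stopping of assessments is an inference. But the inference follows from the single dose, and the other reading still leaves two sections in disagreement. Nothing in the documents available says that follow-up goes on after an SAE.

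A reader might infer three stronger things that the documents do not support.

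- *That SAEs drop out of the safety comparison.* They do not. A co-investigator reviews all adverse events (section 1.3.7). A case of respiratory compromise requiring reversal triggers a DSMB meeting (section 1.3.7). Events needing reversal are counted towards an unblinded analysis (section 1.3.10). Reversal drugs and lowest oxygen saturation are recorded (Appendices C and E).
- *That the rule contradicts intention to treat.* No one is excluded from analysis by section 1.3.7. The rule strains that analysis through missing scores, which is a weaker point.
- *That the bias would favour gabapentin on pain, and by a material amount.* The direction is unknown. A large shift needs several losses, all in one arm, with scores far from the mean. The counts of 5 and 6 events in section 1.3.10 are triggers for review, not expected rates.

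It is also true that many women with an SAE as defined could not mark a VAS or complete a 20-item anxiety scale under any rule. So the loss due to this sentence is smaller than the number of SAEs, at least for the same-day scores. The argument has less force for the day-1 call.

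**Conclusion.** The point holds as a conflict in the text and a likely loss of safety follow-up. It is not a threat to the primary result. On the natural reading, women with an SAE lose the 30-minute and day-1 assessments, and the primary score too if the event comes early enough. The missingness depends on a safety outcome and possibly on arm.

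If the SAE rate is near the documented reversal rate of under 1%, about 0 to 2 of 130 women are affected. Power then stays at about 84%, and the shift in an arm mean from one or two losses is at most 2 × 50 / 65 = 1.5 points against a target of 13. This rests on three assumptions: that reversal is a fair guide to the SAE rate, that lost scores lie within 50 points of the arm mean, and that the rule ends assessments. A drug effect on SAEs would raise the numbers.

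The change is worth making despite the small numbers, because day-1 information that was never collected cannot be recovered at analysis.

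**What to change.** Reconcile sections 1.3.6, 1.3.7 and 1.3.10. In section 1.3.7, replace the statement that women with an SAE are discontinued from the study with text to this effect: *A participant who has an SAE remains in the study. She completes the assessments already scheduled, including the day-1 contact, as her condition and willingness allow, and is analysed in the arm to which she was randomised.*

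- Leave the existing clause on revealing allocation unchanged. Unblinding for care does not require data collection to end.
- Flag any score collected after unblinding.
- Record a score as missing only if it could not be obtained or was refused. Appendix E already has boxes for inability due to sedation and for refusal at the intra-operative and maximum-pain assessments.
- State in section 1.3.10 how missing scores are handled, and align its use of the term SAE with the definition in section 1.3.7.

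The cost is a few lines of text. No assessment is added and the sample size does not change. The one small downside is that some scores may be given after allocation is known, which the flag makes visible.

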1.3.8 Laboratory and other investigations

No laboratory studies will be performed for the clinical trial.

1.3.9 Data management

Data will be collected on paper by the research coordinator. Original documents will be stored in a locked cabinet at the Medstar Health Research Institute. Data will be collected on password protected iPads using the REDCap application for iPad. The iPads and REDCap database will be accessible only by the primary, co-investigators, and research coordinator via password protection. The study personnel who will be collecting and entering the data have extensive experience working with confidential medical information and will follow standard institutional procedures for data handling, verification, cleaning, and storage. Appropriate firewall and virus scanning software are installed and updated routinely by the hospital support staff.

1.3.10 Data analysis

Data analysis will be conducted using Stata. The baseline characteristics of the populations will be described. Intention-to-treat analysis will be performed. Primary continuous outcome (pain score on 100-mm point VAS) for the two treatment groups will be compared using T-tests, and if appropriate, by non-parametric analysis. Secondary outcomes will be compared using Chi-square and T-tests, as applicable. Baseline characteristics will be evaluated for potential interaction or confounding with primary and secondary outcomes. If we observe 5 serious adverse events (SAE) requiring sedation reversal agents before enrolling 50 participants, we will ask the statisticians to unblind allocation and

perform an interval analysis to assess for a relationship between study arm and risk of SAE. Once 50 participants are enrolled, we will ask the same analysis after 6 events occur. These numbers of events are based on the concept that if all of the events are in one treatment arm we would find a statistically significant difference in SAE risk between the arms. For reference, sedation reversal is used in less than 1% of D&Es at both sites. Participants may request that their data not be used for analysis if a request is received prior to analysis as mentioned in the consent form. MedStar Health Research Institute (MHRI) statisticians will be consulted to assist with the analysis as needed.

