1.3.3 Subject recruitment and allocation

A total of 130 participants will be recruited from two sites at the time of abortion provision: MedStar Washington Hospital Center Family Planning and Preventative Care (MWHC) and Planned Parenthood of Metropolitan Washington DC (PPMW). PPMW has a diverse patient population, with a

majority of women being African American and age 20-29 years old. We will recruit from the PPMW clinic on the day they provide second trimester termination procedures. MWHC patients are generally referred from their general obstetrician’s office or self-referred for abortion and are seen in a private outpatient office. We will recruit eligible patients on days when we are not recruiting at PPMW. Baseline characteristics of the outpatient center at WHC and at PPMW in 2012 are shown below:

Table 2: Patient demographics

Age (years)	WHC	PPMW
<20	4%	12%
20-24	11%	38%
25-29	11%	25%
30-39	68%	21%
40 or more	6%	5%
Race		
Black, non-Hispanic	22%	65%
White, non-Hispanic	61%	16%
Hispanic	11%	8%
Multiracial	0%	8%
Other/unknown	6%	3%

In both recruitment settings, D&E is offered as a same-day procedure under moderate sedation with fentanyl and midazolam. Standard care at both sites includes cervical preparation with misoprostol and/or osmotic dilators, initiated at least two hours prior to D&E. Patients will be recruited after gestational age is confirmed to be 14 through 19 weeks, after eligibility for moderate sedation is confirmed, and after patients have provided informed consent for surgical abortion (Appendix A). This occurs after the patient has completed ultrasound, counseling, lab studies, and documentation of medical history. Patients will generally be recruited after initiation of cervical preparation, as this is a time when clinic flow will not be disrupted by study recruitment. Some participants may be recruited before cervical preparation initiation, as clinic flow permits, but no participant will receive study medications until after cervical preparation has begun.

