12) Are you having an abortion because of a fetal diagnosis?

- NO
- YES. Please describe: _____

INTRODUCTION TO VISUAL ANALOG SCALE

For these questions, we are going to ask you to make an X on a line. For example, let's say you are asked how much you like Oreo cookies:

How much do you like Oreo cookies? (make an X on the line)

very little _____ very much

You answer the question by making an "X" on the line according to how much you like or dislike Oreo cookies.

If you liked Oreo cookies a lot, then you might make an "X" on the line like so:

very little _____ X _____ very much

If you liked Oreo cookies more than life itself(!), then you might make an "X" on the line like so:

very little _____ X _____ very much

If you hated Oreo cookies, then you might make an "X" like so:

very little X _____ very much

If you thought Oreo cookies were just "OK," then you might make an "X" like so:

very little _____ X _____ very much

The idea is that if you like Oreo cookies, you make an "X" on the line closer to the phrase "very much;" the closer you make the "X," the more you are saying you like Oreo cookies. If you don't like Oreo cookies, you make an "X" on the line closer to the phrase "very little;" the closer you make the "X," the more you are saying you don't like Oreo cookies.

13) How much do you like Oreo cookies? (make an X on the line)

very little _____ very much

14) How much pain do you experience with your menstrual periods? (make an X on the line)

very little _____ very much

15) How much pain do you anticipate having during your procedure? (make an X on the line)

very little _____ very much

16) How much pain you are experiencing at this time? (make an X on the line)

very little _____ very much

Medical Record Review

1) Date of birth (MM/DD/YYYY): ____ / ____ / ____

2) Gestational age: ____ weeks ____ days

3) Height: ____

4) Weight: ____ kg/lbs

5) Medications administered:

Type: (include antibiotics, misoprostol, uterotonics, pain and nausea medication)	Route -Oral -IV -Rectal -Vaginal -Paracervical	Dose	Timing - Pre-op - Intra-op - Post-op	Time	Notes
 Azithromycin	 Oral	 500 mg	 Pre		
 Alprazolam	 Oral	 0.25 mg	 Pre		

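### The primary t-test is valid but ignores pain scores taken before assignment; one pre-specified covariate-adjusted model could be more precise at almost no cost

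*Combined protocol and SAP*

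**What the plan says.** Section 1.3.10 commits to intention-to-treat and states that the primary VAS score "for the two treatment groups will be compared using T-tests, and if appropriate, by non-parametric analysis". It does not say what would make the non-parametric analysis appropriate. The only text on covariates follows: "Baseline characteristics will be evaluated for potential interaction or confounding with primary and secondary outcomes". It gives no variable list, no model, and no indication of whether an adjusted result would be primary, supportive or exploratory.

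Section 1.3.5 sets the order of events. After consent, the participant completes the Appendix C questionnaire; then "She will then be assigned to the next sequentially numbered randomization packet". Two VAS items in that questionnaire bear directly on the outcome:

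- item 15: "How much pain do you anticipate having during your procedure"
- item 16: "How much pain you are experiencing at this time"

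Section 1.3.3 adds site: "A total of 130 participants will be recruited from two sites at the time of abortion provision". Table 2 shows that the two sites differ in age and race. Neither the randomization text (sections 1.3.1 and 1.3.3) nor section 1.3.10 mentions site.

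**The concern.** Anticipated pain, current pain and site are all fixed before assignment, so adjusting for them cannot bias the treatment comparison. If they predict maximum pain, adjustment removes part of the residual variance and narrows the confidence interval without another participant. The planned test leaves that aside.

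The evaluation of baseline characteristics does not fill the gap. Under randomization, any baseline imbalance is due to chance, so looking for confounding after the data are in is a poor basis for choosing covariates. Nor does the plan say which result would carry the conclusion if the t-test, a rank test and some adjusted model disagreed.

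**Working it through.** **Inputs.** From section 1.3.11: SD 25, difference 13 points, alpha 0.05, power 80%, 59 per arm (118), enrolment 130 (65 per arm if nobody is lost). Sidedness is not stated; two-sided reproduces the plan's figure, while one-sided gives 46 per arm. The multiple correlation r of the covariates with maximum pain is not in the documents and is assumed to lie between 0 and 0.5.

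**The plan's own figure.** n per arm = 2 × 25² × (1.960 + 0.842)² / 13² = 58.05, rounded up to 59. This matches. By the noncentral t distribution, 59 per arm gives 79.98% power, and 60 (59.03 rounded up) are needed for 80%.

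**Adjusted model.** For k covariates and N = 2n:

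- residual SD = 25 × √(1 − r²)
- degrees of freedom = N − 2 − k
- variance factor for chance imbalance = 1 + k/(N − k − 3)
- SE = residual SD × √(2/n × variance factor)
- noncentrality = 13 / SE

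With n = 59 and k = 3 (site, item 15, item 16), the variance factor is 1 + 3/112 = 1.027 with 113 degrees of freedom. Example at r = 0.3: residual SD = 25 × √0.91 = 23.85; SE = 23.85 × √(2/59 × 1.027) = 4.45; noncentrality = 13/4.45 = 2.92; power 82.6%. The unadjusted SE is 25 × √(2/59) = 4.60.

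| Analysis | Residual SD | Power, 59/arm | Power, 65/arm | Detectable difference at 80% power, 59/arm | n/arm for 80% power |
|---|---|---|---|---|---|
| t-test | 25.0 | 80.0% | 83.7% | 13.0 mm | 60 |
| Model, r = 0 | 25.0 | 78.9% | 82.8% | 13.2 mm | 61 |
| Model, r = 0.2 | 24.5 | 80.5% | 84.3% | 12.9 mm | 59 |
| Model, r = 0.3 | 23.8 | 82.6% | 86.1% | 12.6 mm | 56 |
| Model, r = 0.4 | 22.9 | 85.4% | 88.7% | 12.1 mm | 52 |
| Model, r = 0.5 | 21.7 | 89.1% | 91.9% | 11.4 mm | 47 |

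At 59 per arm the model breaks even with the t-test at r of about 0.16.

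**Two covariates only (site and item 15).** At 59 per arm, power is 79.3%, 80.9%, 82.9%, 85.7% and 89.4% at r = 0, 0.2, 0.3, 0.4 and 0.5. Break-even is about 0.13.

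**Simulation check.** With 40,000 runs per setting, the three-covariate model gave 78.9%, 80.7%, 82.3%, 85.5% and 88.5% at 59 per arm, and 82.5%, 84.4%, 86.1%, 88.6% and 91.6% at 65 per arm. All are within 0.6 points of the formula. With no treatment effect, both the model and the t-test rejected 5.1% of the time at 59 per arm.

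**Leaving the choice open.** This was illustrated by a null simulation of 4,000 runs at 59 per arm, with eight assumed covariates. A single t-test rejected 5.1% of the time and one pre-specified adjusted model 5.2%. Taking the better of those two rejected 6.7%. Taking the best of the t-test, a rank test and ten adjusted models rejected about 10%. The plan does not propose such picking; the figures show only what the present wording does not exclude.

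**The case against.** The strongest reply is that nothing is broken. The t-test is valid, the sample size was calculated for it, and the planned 130 give 83.7% power if nobody is lost. The benefit of adjustment rests on a correlation that the documents do not supply: at 0.2 the gain is about half a point, and the gains of 5 to 9 points need 0.4 to 0.5. All of this stands, and it is why the point is a suggestion.

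It can also be said that the baseline sentence already lets these variables in, and that its natural reading keeps the t-test primary. That is fair as far as it goes: the items are not ruled out. But the sentence would admit any baseline variable, in any model, with any weight, and so does not deliver the precision that a named model would.

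Third, item 16 is an uneven baseline. Participants are generally recruited once cervical preparation has begun, but "Some participants may be recruited before cervical preparation initiation, as clinic flow permits", so the item mixes pain before and after preparation starts. This may weaken it as a predictor. It cannot bias the comparison, because the item still precedes assignment, and a model without it performs about as well at the same r.

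**Conclusion.** The point holds as an optional improvement. Pain scores already scheduled before assignment, and site, could sharpen the primary estimate, and the plan names none of them for any analysis. At 59 per arm the effect on power runs from a loss of about 1.1 points (r = 0) to gains of about 0.5, 2.6, 5.5 and 9.1 points at r = 0.2, 0.3, 0.4 and 0.5. These figures assume the plan's SD and difference, a two-sided 5% test and roughly linear covariate effects. Since r is unknown, the claim is only that the model could be more precise. The missing test-selection rule and the undefined status of adjusted results are gaps of detail that the same edit would close.

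**What to change.** In section 1.3.10, before any unblinded analysis:

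- Name one primary analysis: a linear model of maximum-pain VAS on treatment, site, anticipated-pain VAS (Appendix C item 15) and current-pain VAS (item 16), reporting the adjusted difference with its 95% confidence interval.
- Keep the unadjusted t-test as supportive and label any non-parametric test a sensitivity analysis.
- Replace the open-ended confounding evaluation with this fixed list, and label interaction analyses exploratory.
- Restrict covariates to those measured before assignment. The Appendix D pre-operative scores follow study drug and should not be used.
- Fill a missing baseline VAS with the mean of both arms pooled, so that nobody is dropped.

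If the timing of item 16 is a worry, use site and item 15 only. If the investigators prefer to keep the t-test primary, the same model can be named as the single supportive analysis; that settles the status question but forgoes the precision in the primary result.

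The cost is a few sentences, with no new data or participants, and up to about 1 point of power if the covariates turn out not to predict maximum pain.
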